1.0 Objectives*

- As a pain psychologist and palliative care researcher, I developed 1. develop a novel mHealth intervention that harmonizes psychological and pharmacological support for advanced cancer pain. I adapted core components of pain-CBT and integrated them into STAMP (Smartphone Technology to Alleviate Malignant Pain), an existing NINR-funded cancer pain mHealth intervention. STAMP enables patients with advanced cancer to track their pain, opioid use, and side effects. It delivers tailored education and self-management advice while facilitating clinician monitoring and patients' proactive outreach. Having developed an extensive suite of multi-media cancer pain psycho-education covering core pain psychology principles, I seized a strategic opportunity to refine and integrate pain-CBT treatment into medically oriented self-management support in STAMP. Capitalizing on mHealth technology, I strove to destignatize pain psychology through a potentially scalable model that can disseminate behavioral treatments for advanced cancer pain paired with their palliative care pain management plan. My aim is to:
 - Determine feasibility and acceptability of the STAMP+CBT app: up to 15 patients with advanced cancer pain will be recruited from outpatient palliative care clinics at a major cancer center to participate in a single-arm, 6week study of STAMP+CBT (4-week intervention period and a 2-week post intervention period). Surveys at baseline, 4 weeks (end of intervention period), and 6 weeks (end of 2-week post intervention period) will explore trends in pain specific intensity, self-efficacy, and catastrophizing, physical function, opioid use, and quality of life. End-ofstudy interviews will identify facilitators and barriers to usability, acceptability, and satisfaction of the app. The primary outcome will be feasibility evaluating 1) app retention rates and 2) completion of app exercises.

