Participants will include DFCI patients presenting to outpatient palliative care, GCC, or satellite (MV and LD) clinics with ongoing chronic cancer pain management issues. Participants will meet with the study team in person, over the phone, or via a compliant and secure video chat/screen- share platform (i.e. Zoom). We will conduct the pilot cohort with up to 15 patients. Each participant will receive a \$25 gift card upon completion of the 4-week intervention period, and another \$25 gift card upon completion of the 2-week post intervention survey. The first 5 patients will onboard to the application and their involvement/feedback will focus on making final revisions onboarding for the application and study procedures. Therefore, the following 10 patients' data will be included for pilot study analysis and feasibility findings.	 Use the STAMP+CBT mobile app for 4 weeks (intervention period, 4 weeks for content introduction, extended 2 weeks for review of content if patient's request this) Engage with pain CBT content including a goal-setting module, relaxation exercises, and educational content Daily and weekly reporting of pain, catastrophizing, mood, and sleep symptoms and painkiller usage and satisfaction through the app (Appendix U) Complete survey assessments at baseline, 4 weeks (end of intervention period), and 6 weeks (end of 2-week post intervention period) assessing pain severity, self-efficacy and catastrophizing, physical function, opioid use, and quality of life outcomes. (Appendices P, Q, R) End-of-intervention interview (4 weeks) assessing usability and acceptability (Appendix T)
	• Wedical Record Abstraction (Appendix O)

 Table 1. Brief description of pilot cohort activities

PILOT COHORT:

The first few patients (up to 5) will onboard to the application and their involvement/feedback will focus on making final revisions to the mobile application and study procedures. All procedures will be the same for the 15 patients, however, data for the initial patients (up to 5) will not be included in final analysis as their involvement will be focused on revising final app bugs/iterations and modifications to study procedures before the pilot trial initiation. The following patients (up to 10) will be considered as the core pilot study participants to evaluate feasibility and acceptability of the application and study procedures.

Survey assessments

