An RA will ask the patient to complete a baseline survey assessment after consenting, at the end of the 4-week intervention study period, and at the end of the 2-week post intervention period to assess key outcomes (pain severity/interference,⁴² QOL⁴³), potential mediators of intervention effects (catastrophizing⁴⁴, self-efficacy⁴⁵, perceived stress⁴⁶, anxiety/depression⁴⁷, sleep⁴⁸), acceptability,⁴⁹ and usability⁵⁰. The survey can be completed remotely though a link to a Partners Healthcare compliant electronic survey system (e.g. REDCap), over the phone with the RA, over Zoom with the RA,

in person with pen and paper or on a tablet. The Baseline survey will assess socio-demographics, barriers to pain management, pain severity, opioid use, pain and psychological symptoms, and quality of life, with metrics shown in Table 5. End of 4-week intervention period survey will largely replicate the baseline survey; additionally, patients will rate their satisfaction with STAMP+CBT using the 6-item Acceptability E-scale. Surveys will be used to assess pain and psychological symptom trajectory, medication use, and quality of life. See **Appendix P** for the Baseline survey items, **Appendix Q** for 4-week (end of 4-week intervention period) survey items, and **Appendix R** for 2-week (post intervention period) follow-up survey items. Additionally, a subset of patients (up to 10) will be invited for a qualitative interview focused on study burden, facilitators/barriers to app use, satisfaction, and perceived utility in order to guide future refinements to the app (see Appendix T) when they complete use of the app at 4 weeks (end of intervention study period).

Intervention

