 - 9.5.3.5 Cancer type
 - 9.5.3.6 Cancer stage
 - 9.5.3.7 Opioid medications
 - 9.5.3.8 Pain score during last visit (see Appendices O).
 - 9.5.3.9 Health service utilization (e.g. ED visits, hospitalizations, unplanned urgent clinic visits, changes to opioid medications, psychosocial oncology visits)
 - 9.5.4 Survey Assessment Data: Demographic, disease, medication, pain, mood, stress, and sleep data will be collected at baseline before the intervention, end of the 4week intervention, and at the end of the 2-week post intervention period (see Appendices P, Q, R). T1 and T2 of Table 5.
 - 9.5.5 Symptom Reporting: Individual pain, pain interference, pain medication use, stress, mood, and sleep symptoms as well as pain management data will be recorded for each participant over the course of the pilot intervention (Appendix U). Participants will report their symptoms and management daily and weekly.
- *9.6* **Long term follow-up:** Participants in the Pilot Cohort complete a survey assessment assessing quality of life, pain, psychological

measures, healthcare utilization, and app use at the end of the 2 weeks post-intervention (T3 of Table 5).

Measures collected via patient assessments			Survey		App data	Chart review
Assessment	Measure	T1	T2	T3		
Socio-demographics	Standard	Х				
Clinical characteristics	Standard					Х
Baseline cellphone use	MTUAS	х				
Pain	BPI	х	Х	х		
severity/interference						
Opioid use/adherence	Self-report	Х	х	Х		
Quality of life	FACT-G	Х	Х	Х		
Satisfaction	Novel metric		Х			
Use of STAMP+CBT	-		Х	Х	Х	
Usability	SUS		Х			
Management changes	-					Х
Healthcare utilization	-		Х	Х	Х	Х
Self-efficacy in	PROMIS	Х	Х			
managing symptoms						
Self-efficacy in	PROMIS	Х	Х			
managing medications						
Pain catastrophizing	PCS	Х	Х	Х		
Stress	PSS	Х	Х	Х		
Patient reported	PRO-	Х	х	Х		
outcomes	CTCAE					
Depression and	PROMIS	Х	х	х		
Anxiety						
Sleep Disturbance	PROMIS	X	X	Х		

Table 5: Measures collected from patients at each of three survey timepoints

10 Data and Specimen Banking*

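### Section 1.0 and Table 1 promise self-efficacy at baseline, 4 weeks and 6 weeks, but Table 5 schedules both self-efficacy measures at baseline and 4 weeks only

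*Combined protocol and SAP*

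**What the plan says.** Section 1.0 states that surveys at baseline, 4 weeks and "6 weeks (end of 2-week post intervention period) will explore trends in pain specific intensity, self-efficacy, and catastrophizing", followed by physical function, opioid use and quality of life. Table 1 in Section 9.3 lists survey assessments at the same three times, "assessing pain severity, self-efficacy and catastrophizing, physical function, opioid use, and quality of life outcomes".

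The survey paragraph in Section 9.3 describes surveys after consent, at the end of the intervention period and "at the end of the 2-week post intervention period to assess key outcomes (pain severity/interference", with quality of life as the other key outcome. It then names "potential mediators of intervention effects (catastrophizing", self-efficacy, perceived stress, anxiety/depression and sleep), and after these acceptability and usability. It describes the baseline survey "with metrics shown in Table 5". The end of the Intervention text in Section 9.3 sends the reader to the same table for a description of all three surveys.

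The caption is "Table 5: Measures collected from patients at each of three survey timepoints". The table has two self-efficacy rows, one for managing symptoms and one for managing medications, both PROMIS. Each is marked at T1 and T2 only.

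Two nearby sections refer to the table. Section 9.5.4 describes data collected at baseline, at the end of the intervention and "at the end of the 2-week post intervention period (see Appendices P, Q, R). T1 and T2 of Table 5". Section 9.6 describes a survey of quality of life, pain and psychological "measures, healthcare utilization, and app use at the end of the 2 weeks post-intervention (T3 of Table 5"), which fixes T3 as the 6-week survey.

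**The concern.** The Objectives and the table of study activities promise a trend in self-efficacy that runs to week 6. The schedule of measures does not provide for it. Staff who build the 6-week survey from Table 5 would leave self-efficacy out, and an item that was not asked at week 6 cannot be recovered later. The report would then be unable to give a result that Section 1.0 announces.

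The surrounding text does not settle which version is meant. Section 9.5.4 describes three timepoints but cites only two columns of the table. Section 9.6 speaks of psychological measures without naming them.

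**Working it through.** The plan gives no figure to reproduce, and the point depends on no error rate, effect size or sample size. The check sets the outcome lists beside the columns of Table 5.

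**Step 1: the items named in Section 1.0 and Table 1, against Table 5.**

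| Item in the text | Row in Table 5 | T1 | T2 | T3 |
|---|---|---|---|---|
| Pain intensity/severity | BPI | yes | yes | yes |
| Self-efficacy | PROMIS, managing symptoms | yes | yes | no |
| Self-efficacy | PROMIS, managing medications | yes | yes | no |
| Catastrophizing | PCS | yes | yes | yes |
| Opioid use | Self-report | yes | yes | yes |
| Quality of life | FACT-G | yes | yes | yes |
| Physical function | no row of its own | – | – | – |

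Five of the listed items have rows of their own. Four of the five are marked at T3; self-efficacy is the exception.

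**Step 2: all survey rows marked at both T1 and T2.** These are BPI, opioid use, FACT-G, self-efficacy for symptoms, self-efficacy for medications, PCS, PSS, PRO-CTCAE, depression and anxiety, and sleep disturbance: 10 rows. Marked at T3 as well: 10 − 2 = 8. Both rows without T3 are self-efficacy.

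**Step 3: could the blank cells be a fault of text extraction?** This is unlikely. The catastrophizing and stress rows that follow keep their T3 marks. Satisfaction and usability show a sensible T2-only pattern. The same gap appears in both self-efficacy rows.

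**Step 4: how much weight does the survey paragraph in Section 9.3 carry?** Of the five potential mediators that it names, four have T3 and self-efficacy does not. But the same sentence lists acceptability and usability, which Table 5 has at T2 only, so it cannot be read as saying that every item is asked at every survey. The contradiction therefore rests on Section 1.0 and Table 1.

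**Step 5: what remains if Table 5 is followed?** Self-efficacy has two timepoints instead of three. The baseline-to-week-4 change can be computed; nothing can be reported for week 6. The feasibility criterion (modules and surveys completed) and the acceptability criterion (item ratings) in Sections 8.1 and 11.2 do not use self-efficacy.

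**Step 6: instrument labels.** Sections 8.1 and 11.2 speak of pain self-efficacy, and Section 9.3 cites a paper on a pain self-efficacy questionnaire (reference 45). Table 5 lists PROMIS scales for managing symptoms and medications. Section 9.3 says satisfaction is rated with the 6-item Acceptability E-scale, while Table 5 describes the satisfaction measure only as a novel metric. The citations alone do not settle the instrument: Section 9.3 also cites a paper on the Hospital Anxiety and Depression Scale (reference 47) for anxiety and depression, where Table 5 has PROMIS.

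**The case against.** The strongest reply is that Section 1.0 and Table 1 are collective summaries: they name the set of surveys and the set of domains, and do not say that each domain is measured each time. Table 5 is the detailed schedule and should govern. A shorter 6-week survey is also plausible, since Section 9.3 says that the 4-week survey largely repeats the baseline one and makes no such statement for week 6.

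Part of this stands. A shorter 6-week survey may well be intended, and Appendix R, which would show it, is not available. The collective reading is weak, however, because every other item in those two lists that has its own row in Table 5 is marked at T3. If a shorter survey is intended, Section 1.0 and Table 1 promise more than will be collected and still need an edit.

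Three stronger readings are tempting, and the documents do not support them.

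- A reader might infer that the study loses its test of whether an effect persists after the intervention. Sections 9.2 and 9.3 let patients go on using the app in weeks 5 and 6, so week 6 is not a clean off-intervention point even with the data. This is also a single-arm pilot with up to 10 analysed patients.
- A reader might infer that the exploratory engagement analysis in Sections 8.1 and 11.2 fails for self-efficacy. Those sections fix no timepoint for the changes, and baseline to week 4 would serve.
- A reader might infer from Table 5 that the PROMIS scales are the intended measure of pain self-efficacy. The cited questionnaire and the PROMIS scales may not measure the same construct, and the documents do not say which is used.

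**Conclusion.** The contradiction is real and minor. Section 1.0 and Table 1 give self-efficacy three timepoints and Table 5 gives it two. The self-efficacy rows are the only 2 of the 10 rows marked at T1 and T2 that lack T3. If Table 5 is operative, one stated exploratory result, the self-efficacy trend to week 6, cannot be reported.

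This rests on Table 5 having been read correctly from the PDF, which the pattern of the other rows supports. It does not show that data were or will be lost, because the 6-week survey form cannot be seen. The wrong column reference in Section 9.5.4 is a separate small error that holds whichever version is meant. The instrument labels are a question for the authors.

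**What to change.** Choose one of two:

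1. Mark both self-efficacy rows at T3 in Table 5 and include them in the 6-week survey (Appendix R). Cost: two marks in the table and a few more items for each patient at week 6.
2. If a shorter 6-week survey is intended, limit self-efficacy in Section 1.0 and Table 1 to baseline and 4 weeks, and qualify the survey sentence in Section 9.3 to match. Cost: wording only, with no added patient burden.

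In either case, correct Section 9.5.4 to cite T1 to T3 of Table 5.

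Separately, ask the authors to confirm which self-efficacy instrument is used, the questionnaire cited in Section 9.3 or the PROMIS scales in Table 5, and whether the satisfaction measure in Table 5 is the Acceptability E-scale. The wording in Sections 8.1, 9.3 and 11.2 and in Table 5 can then be aligned with their answer. These are text edits.

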2.0 Background*

 Describe the relevant prior experience and gaps in current knowledge. Between 39% to 75% of patients with cancer suffer from pain, with the highest burden of symptoms occurring among those with advanced disease.¹ Poorly managed pain can be devastating to patients' psychological health, physical functioning, social connectedness, and quality of life.^{2,3} Opioids are the cornerstone of treatment;⁴ however, up to 60% of patients experience inadequate relief.^{5,6} Side effects (e.g. constipation and fatigue) are extremely common and often prevent patients from engaging in their

lives.^{7,8} Effective non-pharmacologic treatments are greatly needed to mitigate the burden of advanced cancer pain.⁹

Chronic pain is a multidimensional construct involving dynamic relationships between biological, psychological, behavioral and social factors.¹⁰ Although the biological basis of cancer pain is indisputable, psychological and behavioral factors impact many dimensions of the pain experience.^{11–13} For example: patients' beliefs about pain, self-efficacy, affect, perceived stress, and sleep contribute substantially to pain severity and pain-related disability.^{11–13} Moreover, beliefs surrounding cancer pain and opioid treatment, including stoicism, fears of addiction, and ambivalence undergird patients' many critical pain self-management needs including optimal use of opioids and productive communication with care teams.^{2,14–16} New approaches are needed to address psychological factors that influence cancer pain and opioid use.¹⁷

Numerous psychological treatments have been proven beneficial for chronic non-cancer pain, with growing evidence of benefit for cancer pain.^{18–21} The most efficacious programs address both emotional and evaluative aspects of pain while teaching pain coping skills.^{22–25} Cognitive behavioral therapy for pain (pain-CBT) is the most widely utilized psychological treatment for chronic pain, with meta-analyses demonstrating small to moderate improvements in pain severity and daily functioning.²⁶ Pain-CBT differs from traditional CBT as it targets pain-specific psychological processes through pain psycho-education, cognitive restructuring to challenge maladaptive pain cognitions (e.g. pain catastrophizing), building emotional awareness, and by teaching coping skills to improve physical function and relaxation exercises to reduce muscle tension and stress reactivity.^{27–29}

While the broad goals of pain-CBT are highly relevant to advanced cancer pain, its mode of delivery and certain emphases require modification to be suitable for advanced cancer patients. For example, cognitive restructuring exercises in pain-CBT focus on challenging and modifying "catastrophic" appraisals of pain such as "something must seriously be wrong."²⁷ This is insensitive to advanced cancer patients' realities – for whom worsening pain often truly signifies cancer progression and the terminal phase of illness.³⁰ Another problematic aspect of traditional pain-CBT is its focus on minimizing opioid use, yet this is fundamentally the reverse in advanced cancer where opioids are required. Practically, traditional pain-CBT involves months of in-person therapy, which is too taxing and frankly infeasible for this population. A few studies have sought to modify pain-CBT for general cancer populations. Although they use telehealth to overcome barriers to delivery, these interventions

continue to employ lengthy online sessions (e.g. 45-60 minutes).^{31–33} Early data suggest these programs are feasible and acceptable to patients;^{31–33} however, to our knowledge, none tailor pain-CBT specifically for advanced cancer patients, and none integrate pharmacologic management.²⁰

Mobile health technology (mHealth) is a promising strategy to tailor, deliver, and ultimately disseminate psychological interventions for advanced cancer pain.^{34,35} Mobile health overcomes many of the practical barriers that limit patients' access to traditional behavioral therapies while serving as a logical response to the severe shortages of trained therapists.³⁶ Smartphone delivery co-localizes support at home where patients have the greatest need.³⁷ Developing a smartphone intervention that combines medical support with pain self-management support has great potential for scalability to advanced cancer populations.

2. Development of an mHealth tool to support opioid management for advanced cancer pain. Under the mentorship of Drs. [name] and [name], I have substantially contributed to the development of STAMP, a patient-facing smartphone application and web-based research portal designed to optimize the management of advanced cancer pain with opioids (IRB #18-504). The app hosts patients' specific analgesics (including dose and frequency), which are integrated throughout the application features (e.g. symptom surveys, tailored feedback). Daily surveys assess pain and related symptoms (e.g. pain, opioid use, pain interference, constipation/ laxative use, stress, and sleep) using adaptive survey logic and alternating schedules to minimize survey burden. Patients receive feedback and tailored education based upon their reported symptoms (e.g. links to pain psycho-education), including advice to contact their care team for concerning symptoms. As part of this project, I have led the development of an extensive suite of multi-media cancer pain education covering medication support (e.g. using short and long-acting opioids, managing side effects, opioid safety); pain psychology (e.g. pain perception, pain and the stress response); health behaviors and pain (e.g. sleep hygiene); and skills training (e.g. activity pacing/ relaxation recordings). Content is presented in multiple engaging formats (e.g. written texts with paired illustrations, 2-D animated videos, audio-recordings, games), using real-world examples, everyday language (7th grade reading level), and metaphors to support important concepts (See Appendix C).

In qualitative feedback with 15 patients with advanced cancer pain, the education was considered to be far better than previously received education. Feedback included: "We need to be heard...this is really validating," "the visuals are amazing... I'm able to see a lot

of what you are putting into words," and "the app is intending to move people from...sort of suffering in silence...to find that balance between pain and opioids." The STAMP app is currently being piloted and will be completed by fall 2021.

Qualitative patient interviews regarding pain self-management and attitudes toward psychological treatment. I recently completed in-depth, semi-structured, qualitative interviews with 26 ambulatory advanced cancer patients using opioids to manage chronic pain. The majority (23/26) discussed how stigma of opioids impacted their pain management and willingness to use opioids. Most were also eager for behavioral tools to help manage pain; however, none had any prior exposure. Many expressed that they would be most likely to engage in behavioral treatment if it was recommended by their palliative care/oncology team and integrated into their overarching cancer pain plan. Smartphone delivery was viewed as an attractive way to learn behavioral skills (16/20), as very few patients felt capable of attending traditional in-person therapy. This preliminary data points toward the need for accessible psychological cancer pain support that acknowledges the psychological complexity of opioid-use, while supporting both medical and behavioral aspects of pain self-management.

3. To our knowledge, this will be the first adaptation of pain-CBT content specifically for patients with advanced cancer pain. Existing adaptations of pain-CBT content³² have taught CBT-derived pain coping skills for mixed cancer cohorts,³¹ and for transplant patients.³³ STAMP+CBT now adapts critical components of pain-CBT content to address common concerns of advanced cancer patients, while ensuring a realistic level of engagement for this population. This strategy is conceptually appealing because many pain self-management strategies (e.g. optimal use of breakthrough opioids, engaging in safe physical activity) involve interrelated psychological, behavioral, and medical processes. This approach also destigmatizes psychological treatment for pain, as it is integrated with their opioid management, including support from their cancer care team.

Using smartphones to deliver psychological pain treatment is innovative. Most evidence based, mHealth behavioral pain interventions have utilized tablets^{31,32} and/or video-conferencing to deliver traditional 50-minute, module-based treatments. These interventions do not fully employ the unique capabilities of mHealth to tailor psychological treatments³⁷ and present content in engaging, empathic ways^{38,39} (e.g. through gamification, quizzes). STAMP+CBT will leverage mHealth tailored software to integrate

engaging media (e.g. audio, videos, graphics), and user-centered design (e.g. positive aesthetics, playful interface).

4. STAMP+CBT content and resources were developed in a previous study (IRB 20-453). For the previous study, the team used qualitative feedback and results to help develop modifications to standard pain-CBT content too add them to the original STAMP app for a new pain mobile app that includes cognitive behavioral therapy for pain geared to cancer patients (STAMP+CBT). This section of the study has been completed, all content has been finalized and modifications to the application content for STAMP+CBT have been developed. This content can be reviewed and referenced in appendices D, F, Y, Z.

In the study described above interviews were used because they produce qualitative results; therefore, the portion of the study did not employ statistical analyses. The study team instead reviewed the qualitative feedback from patients and clinicians across three previous cohorts A, B, and C and found common themes. The study team used the common themes from participant responses to guide modifications of the application and its content. The goals of these previous cohorts was to identify and address any problems with the pain-CBT education and resources. For instance, participants requested revising technical psychological labels (e.g. "catastrophizing") to improve literacy, in addition to shortening length of text, adding an option for daily opioid tracking, and increasing the presence of visuals throughout the app. Furthermore, most patients endorsed the content as being usable, informative, convenient to access, and relevant to their cancer pain experiences.

